4.6 Treatment Compliance

Compliance with study treatment will be assessed via relative dose intensity (RDI). Relative dose intensity is defined as 100% times the actual dose intensity (ADI) divided by the intended dose intensity (IDI). Actual dose intensity for a subject is defined as the total dose received over all cycles divided by the sum of the lengths of all cycles in days. The intended dose intensity is the total dose assigned over all cycles divided by the sum of the intended by the sum of the intended lengths of all cycles in days. The assigned dose for a cycle for tivozanib is 1.5 mg/day taken for 3 weeks with 1 week off of study drug. The assigned dose for a cycle for a c

For example, for two cycles of treatment, the intended dose intensity(IDI) for sorafenib would be:

Summaries of ADI, IDI, and RDI will be presented by treatment arm across all cycles as well as for each cycle.

A by-subject listing of study treatment compliance data will also be provided, containing the date of randomization, the date of last dose of study treatment, and the calculated RDI.

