7.2.4 Duration of Study Treatment

Subjects with documented stable disease or an objective response may continue to receive therapy at the same dose and schedule until disease progression or unacceptable toxicities occur, or if other withdrawal criteria are met, as outlined in [Section 11.1](#).

Discontinuation: Subjects experiencing unacceptable toxicities will be discontinued from further study treatment. Subjects with radiological evidence of progressive disease (per RECIST Version 1.1) per investigator/local radiology assessment should continue treatment until progressive disease is verified by an independent radiologist. Images should be submitted for independent review as soon as possible (see Imaging Manual for specific instructions). Verification of progressive disease is not required in the following circumstance:

- Significant clinical deterioration that is compatible with progressive disease.

Subjects who have documented disease progression (as verified by an independent radiologist) will be discontinued from the study treatment.

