3 INVESTIGATIONAL PLAN

3.1 Overall Study Design and Plan

This is a Phase 3, open-label, randomized, controlled, multi-national, multi-center, parallel-arm study comparing tivozanib to sorafenib in subjects with refractory advanced RCC. The study is designed to compare the PFS, OS, ORR, DoR, safety, and tolerability of tivozanib and sorafenib. Approximately 322 subjects with refractory advanced RCC are planned to participate in this study at approximately 160-190 sites. Once informed consent has been obtained and all eligibility criteria have been met (refer to Sections 6.1 and 6.2 of the study protocol for detailed inclusion/exclusion criteria), subjects will be randomized 1:1 using an Interactive Web Response System (IWRS). They will be randomized to treatment with tivozanib or sorafenib, stratified by International Metastatic Renal Cell Carcinoma Database Consortium (IMDC) risk category (favorable; intermediate; poor) and prior therapy (two prior VEGFR TKIs; a prior CeGFR TKI plus any other systemic agent), and must begin treatment within 14 days after randomization. It is anticipated that enrollment to this study will be completed in approximately 15 months.

Tivozanib will be administered orally, at a dose of 1.5 mg/day, beginning on Day 1 of Cycle 1. Subjects will receive tivozanib once daily for 3 weeks followed by 1 week off study drug (1 cycle = 3 weeks on, 1 week off). One cycle will be defined as 4 weeks of treatment. Cycles will be repeated every 4 weeks. Tivozanib should be taken at least 1 hour before or 2 hours after ingesting any food or other medications.

Sorafenib will be administered orally, at an initial dose of 400 mg (two 200 mg tablets) twice daily continuously, beginning on Day 1 of Cycle 1. One cycle will be defined as 4 weeks of treatment. Cycles will be repeated every 4 weeks. Sorafenib should be taken without food at least 1 hour before or 2 hours after ingesting any food or other medications.

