4.8.1 Extent of Exposure

Tivozanib will be administered once a day for 3 weeks, beginning on Cycle 1 Day 1 of each 4-week cycle. Sorafenib will be administered twice a day continuously, also beginning on Cycle 1 Day 1 of each 4-week cycle.

The following summaries will be produced by treatment arm:

- Number of cycles started
- Duration of treatment in days
- Total days drug was received across all cycles and for each cycle
- Total dose administered in mg across all cycles and for each cycle
- ADI, IDI, and RDI across all cycles and for each cycle
- Average daily dose administered in mg across all cycles and for each cycle
- Number and percentage of subjects on treatment by cycle
- Number and percentage of subjects with dose reduction, including a breakdown of reasons for dose reduction
- Number and percentage of subjects with dose interruption, including a breakdown of reasons for dose interruption

Average daily dose administered is calculated as the total dose administered divided by the total number of days on treatment. ADI, IDI, and RDI calculations were described in Section 4.6.

A by-subject listing of exposure data will also be provided.

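### SAP 4.6 does not say how an incomplete last cycle enters actual and intended dose intensity; with a full-cycle intended dose, a mid-cycle stop gives tivozanib the higher relative dose intensity at equal perfect adherence

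*SAP*

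**What the plan says.** SAP 4.6 assesses compliance through RDI, which is 100% times actual dose intensity (ADI) over intended dose intensity (IDI).

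- **ADI** is the "total dose received over all cycles divided by the sum of the lengths of all cycles in days".
- **IDI** starts as follows: "The intended dose intensity is the total dose assigned over all cycles divided by the sum of the intended". The rest of that sentence is garbled in the text available, but it refers to the intended cycle lengths in days.
- **Tivozanib's assigned dose:** "The assigned dose for a cycle for tivozanib is 1.5 mg/day taken for 3 weeks with 1 week off of study drug".
- **Sorafenib's assigned dose** has been lost from 4.6, as has the worked two-cycle IDI example. SAP 3.1 supplies the regimen: "Sorafenib will be administered orally, at an initial dose of 400 mg (two 200 mg tablets) twice daily continuously". It also gives the cycle length for both arms: "One cycle will be defined as 4 weeks of treatment".

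SAP 4.6 and 4.8.1 both report the measure by arm: "ADI, IDI, and RDI across all cycles and for each cycle". Nothing in the surviving text says when the last cycle ends if treatment stops partway through it, or whether the assigned dose and intended length of that cycle are reduced to match.

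**The concern.** Within a cycle, tivozanib's dose is given in the first 21 days and sorafenib's is spread evenly over 28. A full-cycle average is a fair benchmark for both arms only when the cycle is complete.

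Incomplete last cycles should be common. Scans fall every 8 weeks from Cycle 1 Day 1 (Protocol 7.1.5), which is a cycle boundary. A subject with local progression "should continue treatment until progressive disease is verified by an independent radiologist" (Protocol 7.2.4), so dosing can run into the next cycle. Stops for toxicity, clinical deterioration or withdrawal (Protocol 11.1) can fall on any day.

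The stake is the reading of the compliance and exposure tables. RDI is the only measure that SAP 4.6 names for compliance, and comparing tolerability is a secondary objective. Protocol 3.6.2 already reads the earlier trial's dose interruptions and reductions as a sign of better tolerability for tivozanib. A difference produced by the dosing calendar could be read the same way, and an RDI above 100% would look like overdosing when none occurred.

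**Working it through.** The surviving text gives no ADI, IDI or RDI value, so there is no figure of the plan's own to reproduce.

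**Inputs.** Tivozanib 1.5 mg/day for 21 of 28 days (SAP 4.6); sorafenib 2 × 400 = 800 mg/day continuously, and a 28-day cycle (SAP 3.1). Assumptions: perfect adherence, k completed cycles, then a stop on day d of the next cycle.

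**Intended intensity, full cycle.** Tivozanib: 1.5 × 21 / 28 = 31.5/28 = 1.125 mg/day. Sorafenib: 800 × 28 / 28 = 800 mg/day.

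**Formulas**, with L the summed actual cycle length:
- Tivozanib RDI = [1.5 × (21k + min(d,21)) / L] / 1.125
- Sorafenib RDI = [800 × (28k + d) / L] / 800

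**Direction.** If L is the same in both arms it cancels, and the ratio of tivozanib to sorafenib RDI is [28k + (4/3) × min(d,21)] / (28k + d). This exceeds 1 for every stop day from 1 to 27 and equals 1 at d = 28.

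**Example, stop on Day 21 of Cycle 4 (k = 3, d = 21).** Tivozanib dose = 1.5 × 84 = 126 mg.
- Last cycle counted to the stop day, L = 105: 126/105 = 1.2; 1.2/1.125 = 106.7%. Sorafenib: 100%.
- Last cycle counted as 28 days, L = 112: 126/112 = 1.125, or 100%. Sorafenib: 105/112 = 93.8%.

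**Other stop days, tivozanib vs sorafenib:**

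| Stop | Counted to stop day | Counted as 28 days |
|---|---|---|
| Cycle 1, Day 14 | 133.3% vs 100% | 66.7% vs 50.0% |
| Cycle 2, Day 21 | 114.3% vs 100% | 100% vs 87.5% |
| Cycle 3, Day 7 | 103.7% vs 100% | 77.8% vs 75.0% |
| Cycle 5, Day 7 | 102.0% vs 100% | 86.7% vs 85.0% |
| Cycle 6, Day 21 | 104.3% vs 100% | 100% vs 95.8% |
| Cycle 12, Day 21 | 102.1% vs 100% | 100% vs 97.9% |

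The Cycle 1 row is also what the per-cycle table would show for a last cycle ended on Day 14, whatever its number.

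**Third count: last cycle ends at the last dose date.** SAP 3.2.2 ends treatment duration there, though it does not say so for cycle length. The tivozanib rest week then drops out of L even when the last cycle was completed. RDI is 133.3% after one completed cycle, 114.3% after two and 104.3% after six, against 100% for sorafenib.

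**Average size.** Assume exponential time on drug with a 5-month median in both arms and perfect adherence (simulation, 400,000 per arm). Mean overall RDI is:
- to the stop day: 105.8% vs 100%, a gap of 5.8 points;
- as 28 days: 89.3% vs 85.7%, a gap of 3.6 points;
- to the last dose date: 107.1% vs 100%, a gap of 7.1 points.

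**Fourth count: assigned dose, intended length and actual length all cut at day d.** For tivozanib, ADI and IDI are both 1.5 × (21k + min(d,21)) / (28k + d). For sorafenib both are 800. RDI is 100% in both arms for every d.

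**The case against.** The strongest reply is that the damaged part of SAP 4.6 is the part that would show how assigned dose and intended length are built. The surviving tivozanib wording gives a daily rate and a schedule, not a fixed 31.5 mg. It is compatible with cutting IDI at the stop day, and the artefact would then be absent. This stands as a limit. A reader might infer that the formula itself truncates the last cycle, or that IDI is always a full-cycle figure. The text supports neither; it leaves the last cycle undefined. What remains is that every way of counting that cycle favours tivozanib unless IDI is cut as well, and no surviving text says that it is.

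The size can also be overstated. With the design's PFS medians of 6 and 4 months taken as time on drug, the 28-day count gives 90.5% vs 83.6%, a gap of 6.9 points. That figure mixes the calendar effect with unequal treatment durations: with 6 months in both arms it is 90.5% vs 87.3%, or 3.2 points. Day 21 is the worst stop day. If stops follow a boundary scan by about a week (an assumption), the gap is about 2 to 4 points after two to four full cycles. Very early stops pull up the simulated mean: in the stop-day count the median tivozanib RDI is only about 102%.

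Finally, RDI is descriptive. No test or threshold is attached to it, and SAP 4.8.1 and 4.8.2 also report days on drug, dose reductions and interruptions with reasons, and adverse events leading to withdrawal. That lowers the consequence but leaves the named compliance measure uneven between arms.

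**Conclusion.** The point holds as a gap in a derivation rule. SAP 4.6 leaves the incomplete last cycle undefined. With IDI taken as a full-cycle average, as the surviving text reads, a stop before Day 28 gives tivozanib the higher RDI at equal perfect adherence under all three ways of counting the last cycle. With equal exponential time on drug at a 5-month median, the mean overall gap is about 4 to 6 points for the stop-day and 28-day counts, and about 7 if the cycle ends at the last dose. It is about 2 to 4 points for stops near Day 7 after two to four full cycles. The overall gap shrinks as cycles accumulate, while the last cycle's own value in the per-cycle table keeps the full effect. It is zero for completed 28-day cycles unless the last dose date ends the cycle, and zero if IDI is cut at the same day as ADI.

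A reader might infer that the trial's tolerability conclusion or its primary result is compromised. The documents do not support that: PFS inference, alpha and power do not use RDI, and tolerability is described by several other summaries.

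**What to change.** In SAP 4.6, leave completed cycles as defined, so that delayed or lengthened cycles still lower RDI. For the last cycle, cut three quantities at one prespecified day: the assigned dose on each arm's own schedule, the intended length and the actual length. Define that day the same way in both arms, for example the recorded date of the decision to discontinue, or the last dose date if that is what is collected. The two dates differ when an interruption ends in discontinuation. With the last dose date, that final gap in dosing leaves no mark on RDI, so the choice should be stated. Apply the rule to the overall and the per-cycle tables in SAP 4.6 and 4.8.1. Perfect adherence then gives 100% in both arms at any stop day.

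The cost is a change of SAP wording and one derivation. If the date of the decision is not recorded, the last dose date avoids any new data. Reported tivozanib RDI may be slightly less favourable.

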4.7 Efficacy Evaluation

4.7.1 Analysis and Data Conventions

This study is designed to test for superiority. The null hypothesis will be that there is no difference between tivozanib and sorafenib in median PFS. The alternative hypothesis will be that there is a difference. Symbolically, this is expressed as follows:

H₀: $mPFS_{tivozanib} \le mPFS_{sorafenib}$

H_a: $mPFS_{tivozanib} > mPFS_{sorafenib}$

A one-sided, log-rank test stratified for IMDC risk category (favorable vs. intermediate vs. poor) and prior therapy (two prior VEGFR TKIs vs. a prior checkpoint inhibitor plus a prior VEGFR TKI vs. a prior VEGFR TKI plus any other systemic agent) at a significance level of $\alpha = 0.025$ will be used to test this hypothesis.

Estimates of the hazard ratio (HR) for treatment and the corresponding 95% CI will also be presented. They will be estimated using the stratified Cox proportional hazards model with sorafenib as the reference group and stratification factors IMDC risk category and prior therapy.

4.7.1.1 Multi-center Studies

For the purpose of the summaries and analyses mentioned in this SAP, the term 'Center' will be used to define each investigator site.

All centers will be pooled together in the efficacy analyses. If the results reveal impact of the centers, then ad hoc analyses will be performed. In that case, the centers may be grouped by geographic regions (see Section 4.5) and evaluation of the consistency of treatment effects across geographic regions may be performed.

4.7.1.2 Adjustments for Covariates

The potential influences of baseline characteristics and stratification factors on the primary PFS endpoint will be evaluated. These factors include the following:

- Age categorization (<65, >= 65 years)
- Race (White, Non-white)
- Gender (Male, Female)
- Baseline Eastern Cooperative Oncology Group (ECOG) performance status (0, 1)
- Time from initial diagnosis to randomization (< 1 year, >=1 year)
- Geographic region [North America (NA), European Union (EU), Rest of World]

- IMDC risk category (Favorable, Intermediate, Poor)
- Prior therapy (Two Prior VEGFR TKIs, Prior Checkpoint Inhibitor Plus VEGFR TKI, Prior VEGFR TKI Plus Other Systemic Agent)
- Number of metastatic sites involved (1, >=2)
- Baseline systolic blood pressure (<=140 mmHg, >140 mmHg)Baseline diastolic blood pressure (<=90 mmHg, >90 mmHg)

To assess the robustness of study conclusions to the choice of covariates, a sensitivity analysis will be performed.

4.7.1.3 Handling of Dropouts or Missing Data

In general, imputed partial dates will not be used to derive study day, duration (e.g., duration of adverse events), or elapsed time variables. In addition, imputed dates are not used for deriving the last contact date in the overall survival analysis dataset.

Imputed dates will not be displayed in listings unless otherwise stated.

The partial date imputation will follow ADaM conventions. The ADaM approach is to populate the numeric date variables with the imputed date and add a flag variable to the dataset that indicates the level of imputation.

The flag variable can contain the values: blank, 'D', 'M', 'Y'.

blank: indicates that no imputation was done

- D='Day': indicates that the day portion of the date is imputed
- M='Month': indicates that the month and day portions of the date are imputed
- Y='Year': indicates that the entire date (year, month, and day) is imputed

Imputing partial AE and prior/concomitant medication start dates:

- a) If the year is unknown, the date will not be imputed and will be assigned a missing value.
- b) If the month is unknown, then:
 - 1. If the year matches the first dose date, then impute to the month and day of the first dose date.
 - 2. Otherwise, assign 'January'.
- c) If the day is unknown, then:
 - 1. If the month and year match the first dose date, then impute to the day of the first dose date.
 - 2. Otherwise, assign '01'.

Imputing partial AE and prior/concomitant medication stop dates:

- a) If the year is unknown, the date will not be imputed and will be assigned a missing value.
- b) If the month is unknown, then assign 'December'.
- c) If the day is unknown, then impute to the last day of the month.

Imputing partial death dates:

- a) If the month and/or year are unknown, the death date will not be imputed and the subject will be censored for overall survival at the last known date alive.
- b) If the day is missing, then assign '01'.
- c) If imputing the first day of the month results in a negative overall survival time, the subject will be censored for overall survival at the randomization date.

A subject data listing will be provided showing all subjects with missing values for the primary endpoint. For these subjects, the listing will provide all observed data relating to the primary endpoint (i.e. all measurements recorded prior to the missing value, any measurements recorded after the missing value, important baseline characteristics, the recorded reason for study discontinuation, and the date of study discontinuation). The listing will also provide the imputed date(s) used in the primary analysis.

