Any medication that a subject takes other than tivozanib or sorafenib during the duration of treatment is considered a concomitant medication. Information regarding the usage of concomitant medications will be collected throughout participation in this study, starting from the time the subject signs the informed consent form until a period of 30 days after the last dose of study drug. For each concomitant medication taken during the study, the generic component will be identified using the World Health Organization Drug (WHO Drug) Dictionary.

Physical Examination

A complete physical examination (PE) will be performed at screening by a physician or staff member who is qualified to perform such examinations. The complete PE will entail a thorough review of all body systems, including weight (kg) and height (cm). The remaining PE assessments will be directed PEs, but must include weight (kg). They will be done in a targeted manner, covering body systems related to the subject's disease or relevant findings in the complete PE.

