4.8.3 Prior and Concomitant Medications

All medications will be collected from the time the subject signs the informed consent form throughout the subject's participation in the study, including a period of 30 days after the subject's last dose of study drug.

For each concomitant medication taken during the trial, the generic component will be identified using the World Health Organization Drug Dictionary (WHO-DD; WHODDB3 ENHANCED JUN 2015).

Medications will be assigned to a time period (prior and/or concomitant) as follows:

- If both the start and stop date exist and are before the first dose date of study drug, the medication will be counted as prior.
- If the start date is on or after the first dose date of study drug, the medication will be counted as concomitant.

- If the start date is before the first dose date of study drug and the stop date is after the first dose date of study drug or the medication is continuing, the medication will be counted as prior and concomitant.
- If the start date is missing and the stop date is before the first dose of study drug, the medication will be counted as prior.
- If the start date is missing and the stop date is after the first dose of study drug or the medication is continuing, the medication will be counted as concomitant.
- If the start and stop dates are missing, the medication will be counted as concomitant.

Summaries showing number of subjects and percentage taking each medication will be provided for each preferred medication term by treatment arm. This will be done separately for prior and for concomitant medications.

A by-subject listing of all prior and concomitant medication data will also be provided.

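### A medication whose partial start date matches first dose, and which has a recorded stop before dosing, is tabulated as concomitant because the imputed start is not capped at the stop date

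*SAP*

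**What the plan says.** SAP 4.7.1.3 gives separate rules for partial start dates and partial stop dates of adverse events and of prior and concomitant medications.

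- Start, day unknown: "If the month and year match the first dose date, then impute to the day of the first dose date". Any other month goes to its first day.
- Start, month unknown: "If the year matches the first dose date, then impute to the month and day of the first dose date". Any other year goes to January.
- Start, year unknown: left missing.
- Stop, day unknown: "If the day is unknown, then impute to the last day of the month". With the month unknown, December is assigned.

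No start rule refers to the stop date, and no later clause reconciles the two. The section does limit where imputed dates may be used: "In general, imputed partial dates will not be used to derive study day, duration (e.g., duration of adverse events), or elapsed time variables". It also keeps them out of the last contact date for OS. Assignment to prior or concomitant is not among the excluded uses.

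SAP 4.8.3 then assigns each medication to a period:

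- Prior: "If both the start and stop date exist and are before the first dose date of study drug, the medication will be counted as prior".
- Concomitant: "If the start date is on or after the first dose date of study drug, the medication will be counted as concomitant".
- Wholly missing start: "If the start date is missing and the stop date is before the first dose of study drug, the medication will be counted as prior".

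The definition behind these rules is in SAP 3.2.2: "Any medication that a subject takes other than tivozanib or sorafenib during the duration of treatment is considered a concomitant medication".

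**The concern.** Imputing an uncertain start to the first-dose date is reasonable when use on treatment is possible. When the recorded stop already precedes first dose, on-treatment use is ruled out, yet the rule still places the start on the day of first dosing. The derived record then starts after it ends.

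The result is also incoherent. With no start date at all, SAP 4.8.3 uses the stop date and gives the right answer. With a start month that happens to be the first-dose month, it ignores the stop date and gives the wrong one, so better data lead to a worse classification.

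At stake is the accuracy of the two medication tables in SAP 4.8.3. Medications are collected from consent (Protocol 7.3) and screening covers the 21 days before first dose (Protocol 7.1), so drugs stopped shortly before dosing are within the data collected. SAP 4.7.1.3 keeps imputed dates out of listings unless otherwise stated. A reader could therefore see a pre-dose stop in the listing and a concomitant count in the table, with nothing to explain the difference.

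**Working it through.** The plan states no figure on this point, so there is none to reproduce. The check follows the rules as written.

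**General argument.** Let F be the first-dose date, S the imputed start and E the known stop, with E before F. When the partial start matches F on month and year, or on year alone with the month unknown, SAP 4.7.1.3 sets S = F.

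1. Prior requires S < F and E < F. Since S = F, this fails whatever E is.
2. Concomitant requires S ≥ F. Since S = F, this is met whatever E is.
3. So every such record with E < F is classed as concomitant.
4. With a cap, S' = min(S, E) = E < F. Both parts of the prior rule hold, and the record is classed as prior.

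**Test records.** F = 20 March 2017 is an assumed date, chosen for illustration.

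| Recorded start | Recorded stop | Start used | Class as written | Class with cap |
|---|---|---|---|---|
| Mar 2017, day unknown | 10 Mar 2017 | 20 Mar 2017 | concomitant | prior |
| 2017, month unknown | 15 Feb 2017 | 20 Mar 2017 | concomitant | prior |
| 2017, month unknown | Feb 2017, day unknown (imputed 28 Feb) | 20 Mar 2017 | concomitant | prior |
| wholly missing | 10 Mar 2017 | missing | prior | prior |
| 5 Mar 2017 (complete) | 10 Mar 2017 | 5 Mar 2017 | prior | prior |
| Feb 2017, day unknown | 10 Mar 2017 | 1 Feb 2017 | prior | prior |
| 2016, month unknown | 10 Mar 2017 | 1 Jan 2016 | prior | prior |
| Mar 2017, day unknown | 25 Mar 2017 | 20 Mar 2017 | concomitant | concomitant |
| Mar 2017, day unknown | Mar 2017, day unknown (imputed 31 Mar) | 20 Mar 2017 | concomitant | concomitant |

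The first three rows show the fault. The next four show that complete, wholly missing and non-matching partial starts are classified correctly. The last two show that the cap leaves a record alone when its stop, known or imputed, falls after first dose.

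**Enumeration for the same F.**

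- Day unknown: the possible earlier stop dates run from 1 to 19 March, so 20 − 1 = 19. All 19 give concomitant as written; with the cap, 0 are wrong.
- Month unknown: they run from 1 January to 19 March, so 31 + 28 + 19 = 78. All 78 give concomitant as written; with the cap, 0 are wrong.

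The counts depend on the assumed F. Day unknown ranges from 0 (first dose on the 1st) to 30 (on the 31st). Month unknown ranges from 0 (1 January) to 365 (31 December of a leap year). The proportion misclassified is 100% in each case. These are counts of possible stop dates, not of records in the trial.

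**The case against.** **Partial could be read as missing.** SAP 4.8.3 does not cite 4.7.1.3, so its rule for missing starts might be taken to cover partial ones. This is weak. SAP 4.7.1.3 expressly imputes medication start dates and leaves them missing only when the year is unknown.

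**The intent is clear.** The SAP 3.2.2 definition already excludes a drug stopped before dosing, so this is a drafting gap and not a chosen method. That is fair, but the stated algorithm is what will be programmed, and it contradicts the definition.

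**Adverse events.** A reader might infer that the same uncapped rule makes screening events that resolved before dosing treatment-emergent. The documents do not support this. SAP 4.8.2 refers to the imputation and then qualifies it: an event is not treated as emergent when a comparison of partial dates clearly shows that it began before first dose. A resolution date before dosing is such evidence. SAP 3.2.2 adds that an event already recorded before treatment counts only if its grade rises. Medications have no counterpart to either safeguard.

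**Deviations and the per-protocol set.** A reader might also infer false prohibited-medication deviations, and from them per-protocol exclusions. Nothing links the 4.8.3 flag to deviation status. SAP 4.3.2 places the definition of major deviations in separate specifications, with final determination before database lock. Prior antineoplastic treatments, with start and end dates, are recorded under Disease History in Protocol 7.1, and the documents do not show that they pass through the 4.8.3 rule.

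**Materiality.** The affected output is descriptive and the rule is the same in both arms. This stands, and it limits the weight of the point.

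**Conclusion.** The point holds for medications only. Under the rules as written, a medication is wrongly counted as concomitant when three conditions meet: its start date is partial; the known part matches first dose on month and year, or on year alone with the month unknown; and its stop date precedes first dose. Every such record is misclassified, and no other section corrects it.

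The shown effect is confined to the descriptive prior and concomitant medication tables. No effect on PFS, OS, any error rate, the treatment-emergent event tables or the per-protocol set is shown. The number of affected records cannot be estimated, because the documents give no count of partial dates. The conclusion assumes that the 4.7.1.3 imputed dates feed the 4.8.3 assignment, which is the natural reading of a rule written for medication start dates. It is a minor fault, but a definite one, and worth correcting.

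**What to change.** Add to SAP 4.7.1.3, with a cross-reference in 4.8.3: an imputed medication start date may not be later than the known or imputed stop date, and a medication whose stop date is before first dose is counted as prior whatever its imputed start. Apply this before the 4.8.3 assignment.

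The cost is one SAP sentence and one line of derivation code. No new data are needed, and the correctly classified test records kept their class.
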